### 1. SYNOPSIS

Study Title	SleepSure: a randomised controlled trial to assess the effects of eye masks and earplugs on the quality of sleep for patients in hospital.			
Internal ref. no. / short title	SleepSure: a study aimed at improving sleep for hospital inpatients			
Study Design	Randomised Controlled Trial			
Study Participants	Patients admitted to adult general medical and surgical wards at Oxford University Hospitals NHS Foundation Trust			
Planned Sample Size	400			
Planned Study Period	01 February 2016- 31 January 2017 Pilot data collection 01 February 2016 to 14 February 2015 Recruitment 01 March 2016 – 31 May 2016 (last follow-up 14 June 2016)			
	Objectives	Outcome Measures		
Primary	Do earplugs and eye masks help hospital patients to sleep better?	SleepSure Questionnaire, based on the validated Richards-Campbell Sleep Questionnaire		
Secondary	Does the use of earplugs and eye masks lead to a reduced length of stay, reduced incidence of falls or reduced use of sleep aid medication? How many patients provided with earplugs and an eye mask choose to use them?	Length of stay (days) Number of falls recorded during stay Doses of zopiclone (sleeping tablet) used to help sleep during stay Use of earplugs and eye masks (SleepSure sleep questionnaire)		

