#### The question

Our question is simple: Does the provision of earplugs and eye masks improve the sleep of hospital inpatients?

Secondary questions are whether this provision leads to a reduced length of stay, reduced incidence of falls and reduced use of sleep aid medication. We also wish to discover how many patients provided with earplugs and an eye mask choose to use them.

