### 4. OBJECTIVES AND OUTCOME MEASURES

Objectives	Outcome Measures	Timepoint(s) of evaluation of this outcome measure (if applicable)
Primary Objective Do ear plugs and eyemasks improve inpatient experience of sleep?	SleepSure sleep questionnaire	Questionnaire given >1 day after recruitment
Secondary Objectives A) How many patients provided with eye masks and earplugs choose to use them?	SleepSure sleep questionnaire	Questionnaire given >1 day after recruitment
B) Does the use of earplugs and eye masks lead to reduced length of stay?	Length of stay data from hospital administration system	After discharge
C) Does the use of earplugs and eye masks lead to reduced use of sleep aid medication?	Drug chart data from electronic records.	After discharge
D) Does the use of earplugs and eye masks lead to a reduced incidence of falls?	Falls data from centrally collated routinely collected information	After discharge

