# 7.2. Informed Consent

Each patient considered eligible will be given a patient information sheet by a nurse on the ward, part of the direct care team. Following this they will be approached by the SleepSure research nurse who will give them a short verbal explanation that will cover:

- The goal of the study (i.e. to study how to improve sleep)
- The trial intervention (i.e. aircraft style earplugs and eye mask)
- The fact that only a 50% chance of getting intervention (random allocation)
- The collection of data (one questionnaire) >1 day after recruitment
- The collection and use of some routine hospital data (falls, use of sleeping tablets, length of stay)
- The option to withdraw consent at any time
- The specific action of having being presented with a SleepSure Questionnaire >1 day after recruitment, which if not filled in will be taken as a refusal of consent for the use of that data in the trial.

A written consent form will be used.

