#### 7.6. Subsequent Visits

At the final visit (>1 day after recruitment) the SleepSure research nurse will provide a SleepSure Questionnaire. After discharge the participant's anonymised ID number, age, gender, date of admission, date of discharge, length of stay, number of falls, doses used of zopiclone will be extracted from the notes and recorded by the SleepSure research nurse onto an Excel spreadsheet stored in a secure location on the Trust network with access only via a password-protected computer. The results of the SleepSure questionnaire will also be recorded onto this secure document at this time. (Please see section 11 for more information.)

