# **10.1.** Description of Statistical Methods

There will be no interim analysis.

The primary analyses will be to compare the two groups on all items collected, using t-test and Mann-Whitney U tests as appropriate with two-tailed testing (i.e. accepting that harm is also possible). The expectation is that the intervention group will have:

- Better sleep on the questionnaire
- Less use of night sedation over their hospital stay
- Less falls over their hospital stay
- A shorter length of stay

Secondary analyses will investigate:

- Variation between wards on all measures, irrespective of patient group.
- Reported use of and problems with the earplugs and eye masks.

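### The secondary question is about sleep medication in general, but only zopiclone doses are collected, so it can be answered for zopiclone alone

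*Combined protocol and SAP*

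**What the plan says.** The question is put at the level of a class of medicines wherever it is asked:

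- Section 1 (Synopsis), secondary objective: "reduced incidence of falls or reduced use of sleep aid medication".
- Section 3, The question: "reduced incidence of falls and reduced use of sleep aid medication".
- Section 4, objective C: "Does the use of earplugs and eye masks lead to reduced use of sleep aid medication". The outcome measure beside it is "Drug chart data from electronic records", with no drug named.
- Section 7.2, what patients are told will be collected: "The collection and use of some routine hospital data (falls, use of sleeping tablets, length of stay".
- Section 10.1, the expected result in the intervention group: "Less use of night sedation over their hospital stay".

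The measurement is one drug:

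- Section 1 (Synopsis), outcome measure: "Doses of zopiclone (sleeping tablet) used to help sleep during stay".
- Section 7.6, the extraction list: "doses used of zopiclone will be extracted from the notes". No other medicine is on that list.

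No section lists the medicines that count as sleep aids, says that zopiclone is the only or main one used on these wards, gives a reason for using it as a proxy, or says how other sleep medicines are handled.

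**The concern.** The objective and the planned interpretation are wider than the variable collected. A reader of the results would naturally take a difference in zopiclone doses as the answer to the question about sleep medication, because Section 10.1 states the expectation in those broader terms.

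Two things are at stake. First, use of other sleep medicines is invisible, so some users would be indistinguishable from non-users. That lowers the observed rate of use and the power to see a difference. Second, if prescribing moved from zopiclone to another medicine, or the reverse, the data could not separate that from a real change in overall use.

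The gap may be hard to close later. Section 11.2 has the log linking study numbers to hospital numbers destroyed within 3 months after the study ends.

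**Working it through.** **1. What each kind of patient contributes under Section 7.6 as written**

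| Sleep medicine received | Recorded zopiclone doses | Effect on the class-level question |
|---|---|---|
| None | 0 | Correct |
| Zopiclone only | True count | Correct |
| Another medicine only | 0 | Cannot be told apart from no use |
| Zopiclone and another | Zopiclone count only | Still counted as a user, but doses under-counted |

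A patient moved from zopiclone to another medicine contributes fewer doses even if total use is unchanged.

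**2. Effect on the comparison if under-capture is the same in both arms**

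Let p be the true proportion of controls given any sleep medicine, R the true relative risk, and c the share of users identified through zopiclone.

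- Observed control risk = c × p.
- Observed intervention risk = c × R × p.
- Observed relative risk = (c × R × p) / (c × p) = R, so it is unchanged.
- Observed absolute difference = c × p × (1 − R), so it shrinks in proportion to c.

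Power therefore falls as c falls. If c differed between arms, the relative risk would be biased, in a direction that cannot be predicted from the documents.

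**3. Size of the power loss (illustration only)**

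There is no figure in the plan to reproduce: Section 10.2 gives 400 as a recruitment estimate, with no effect size, event rate or power.

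Inputs:

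- n = 200 per arm: 400 (Section 10.2) split by equal-chance allocation (Section 7.4).
- Two-sided testing: Section 10.1. The 5% level is assumed.
- p = 20%, R = 0.6 (a 40% relative reduction) and c = 100%, 80% or 60%: all assumed.

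Formula: h = 2·arcsin√(control risk) − 2·arcsin√(intervention risk), and power = Φ(h·√(n/2) − 1.96). With n = 200, √(n/2) = 10.

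| c | Control risk | Intervention risk | Difference | h | 10h − 1.96 | Power |
|---|---|---|---|---|---|---|
| 100% | 20.0% | 12.0% | 8.0 points | 0.220 | 0.24 | 59% |
| 80% | 16.0% | 9.6% | 6.4 points | 0.193 | −0.03 | 49% |
| 60% | 12.0% | 7.2% | 4.8 points | 0.164 | −0.32 | 38% |

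With p = 30% and the same R, power is 81%, 69% and 54%. The pattern is the same from a higher starting point.

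This models any use against no use. The plan compares doses by t-test or Mann-Whitney test, so these figures show direction and rough scale only and are not the power of the planned analysis.

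**4. Data source**

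Section 4 names the electronic drug chart as the source for objective C, while Section 7.6 says the notes. The two do not agree on where the count comes from.

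**The case against.** **The restriction was specified in advance.** The synopsis sets zopiclone doses beside the broader objective, and measuring a broad aim by one countable variable is a common design choice. This stands in part. A reader might infer that the question is left unanswered altogether. The documents do not support that, because it is answered for zopiclone, the measure the synopsis names. Pre-specification does not widen what that measure shows, however, and Section 10.1 still frames the result as night sedation.

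**Other medicines do not always count as zero.** This stands. Only patients given another sleep medicine and no zopiclone become indistinguishable from non-users. Those given both are under-counted.

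**The power figures rest on assumptions.** This also stands. The rates, the effect and the capture share are all assumed, and the endpoint is not the planned one. The share of users may also exceed the share of use, because patients given both are still identified, which would make the loss smaller. Section 10.3 excludes patients without a questionnaire, so 200 per arm is optimistic. Even with full capture, power is only 59% at 20% use, so much of the shortfall has nothing to do with zopiclone.

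**Bias from switching is speculative.** A reader might infer that the comparison is biased. The documents give no evidence that prescribing would shift by arm. What stands is narrower: if it did shift, these data could not show it.

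**A wider definition invites judgement.** The research nurse who opens the envelope (Section 7.4) also extracts the data (Section 7.6). Deciding case by case whether an as-needed medicine was given for sleep would be an unblinded judgement, which a single named drug avoids. This is a fair point, and a fixed list meets it.

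**Conclusion.** The mismatch is real and can be read directly from the text. As written, the trial can report on zopiclone use but not on sleep medication in general, and it cannot tell substitution from reduction. If under-capture is equal in both arms, the relative risk is preserved and the cost is power. How much is unknown, because the documents give neither the rate of sleep medicine use nor zopiclone's share. If zopiclone were nearly all of the use on these wards, little would be lost, but the protocol does not say so.

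This affects one secondary outcome. It is worth correcting because the remedy is cheap and participants' records are already being read after discharge.

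**What to change.** In the synopsis and Section 7.6, replace the zopiclone-only item with doses of every medicine on a short list of sleep medicines, extracted from the electronic drug chart for both arms. Fix the list before extraction starts and count every listed medicine by rule, so that the unblinded research nurse makes no judgement about indication. Analyse any use (yes/no) and the number of nights with a dose, which allows different medicines to be combined. Keep zopiclone doses as a sub-item.

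The cost is slightly more extraction time and the writing of the list. The downside is that some listed medicines may have been given for another reason.

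If the list is not adopted, limit the secondary objective (Sections 1, 3 and 4), the Section 10.1 expectation and the conclusions to zopiclone use, and say why it is an adequate proxy if it is to be read as one. This is a wording change only.

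In either case, reconcile Section 4 and Section 7.6 on the data source, and make the description in Section 7.2 match what is collected.

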### 6.2 Inclusion criteria:

Eligible candidates at the point of enrolment must:

- Be 18 years of age
- Be expected to stay in Oxford University Hospitals NHS Foundation Trust for at least one more night
- Be able to understand and use earplugs and eye mask.
- Have basic understanding of English reading and writing.
- Be considered likely to have the Mental Capacity to give consent for use of personal data in the study at the point of filling in the SleepSure Questionnaire (>1 day after recruitment). NB/ Data will not be collected from individuals who are unable to give consent with the filling in of the SleepSure questionnaire.
- Be expected to be able to fill in the SleepSure Questionnaire with or without assistance

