# 7.4. Randomisation, blinding and code-breaking

Every patient recruited will first be registered by the SleepSure research nurse onto an electronic password-protected Participant ID log in a secure location on the Trust network. This will generate a trial number (e.g. WPH WdA 007 [hospital, ward, number]).

Randomisation:

Using a random number generator performing simple randomisation opaque numbered envelopes will be filled with a piece of paper stating control or intervention with an equal chance of each individual envelope containing a control or an intervention instruction. 50 sealed envelopes will be stacked into a box on each ward, each with a unique identifier number on the outside. When a potential participant is identified the SleepSure research nurse will go to the next envelope in the box and open it to determine if the patient is in the control or intervention arm.

If the patient is allocated to the trial arm, the research nurse will give the patient a set of earplugs and an eyeshade, and explain their use, checking that the patient can use and remove them safely giving instruction as required. The earplugs and eye mask will then be placed into a transparent plastic wallet, labelled with the patient's name, the study and placed within easy reach of the patient.

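### Sections 4 and 7.6 name different sources for falls, length of stay and zopiclone use, which leaves falls in particular open to avoidable unequal ascertainment by unblinded staff

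*Combined protocol and SAP*

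**What the plan says.** The outcome table in section 4 gives each secondary outcome its own routine source. For stay it is "Length of stay data from hospital administration system"; for sleep medication, "Drug chart data from electronic records"; for falls, "Falls data from centrally collated routinely collected information".

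Section 7.6 describes the same items differently. After discharge, length of stay, number of falls and zopiclone doses "will be extracted from the notes and recorded by the SleepSure research nurse", who enters them in a spreadsheet.

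Section 7.4 shows what that role knows. When a participant is identified, "the SleepSure research nurse will go to the next envelope in the box and open it", and for a patient in the intervention arm "the research nurse will give the patient a set of earplugs and an eyeshade, and explain their use". The heading of 7.4 mentions blinding, but the text under it describes none.

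Section 7.6 also has the research nurse provide the SleepSure questionnaire, which is the primary outcome. Section 6.2 requires that patients "Be expected to be able to fill in the SleepSure Questionnaire with or without assistance". No section says who may assist.

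**The concern.** Two people following this protocol could build different datasets for the same outcomes, one from system records and one from reading notes. That needs correcting whatever one thinks about bias.

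The route in 7.6 also leaves room for judgement. How hard someone looks for a fall in free-text notes can depend on knowing the arm. Section 10.1 states the direction the team expects, including fewer falls with the aids. Section 3 (risk 5) says it is conceivable that the aids cause falls, and section 9.1 records no adverse events other than falls and deaths. Looking less hard in the intervention arm could therefore mimic benefit and hide a foreseen harm; looking harder there would do the reverse.

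For the primary outcome, help from someone who knows the arm could move a subjective sleep rating. Section 13.7 discusses expectation bias, but only in terms of what controls might be offered, not who collects outcomes.

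**Working it through.** **Sources side by side**

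| Outcome | Section 4 | Section 7.6 | Room for judgement |
|---|---|---|---|
| Length of stay | Administration system | Notes | Small: follows from two dates |
| Zopiclone doses | Electronic drug chart | Notes | Small: count of charted doses |
| Falls | Centrally collated routine data | Notes | Larger: depends on search and reading |

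The notes could be taken to include the electronic drug chart. They do not naturally include the administration system or a central falls collection.

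**Inputs for size.** The plan gives 400 patients (section 10.2), equal allocation probability (7.4) and two-tailed tests (10.1). It gives no alpha, SD, effect size, fall rate or assisted share, so it has no figure of its own to reproduce. Assumed here: 200 per arm, two-sided alpha 0.05, no true effect, normal approximation.

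**Falls** (patients with at least one fall). With true risk p in both arms and capture of 95% in controls and 75% in the intervention arm, the recorded risks are p1 = 0.95p and p2 = 0.75p, a ratio of 0.75/0.95 = 0.79. The rejection probability is Φ((d − c)/se1) + Φ((−d − c)/se1), where d = p1 − p2, m = (p1 + p2)/2, c = 1.96 × √(2m(1 − m)/200) and se1 = √((p1(1 − p1) + p2(1 − p2))/200).

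- p = 3%: recorded 2.85% v 2.25%, d = 0.006, c = 0.0309, se1 = 0.0158. Φ(−1.58) + Φ(−2.34) = 0.057 + 0.010 = 6.7%.
- p = 5%: recorded 4.75% v 3.75%, or 9.5 v 7.5 patients out of a true 10 per arm. By the same formula, 7.9%.
- With a milder gap of 95% v 85%: 5.4% at p = 3% and 5.7% at p = 5%.

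**Questionnaire.** A between-arm shift of b SD across the whole arm gives z = b/√(2/200) = 10b, and a false-positive rate of Φ(z − 1.96) + Φ(−z − 1.96).

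- b = 0.02: z = 0.2; 0.039 + 0.015 = 5.5%.
- b = 0.05: z = 0.5; 0.072 + 0.007 = 7.9%.
- b = 0.10: z = 1.0; 0.169 + 0.002 = 17.0%.

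Help affects only patients who receive it. If each assisted patient's answer moved by 0.10 SD, an assisted share of 20% gives b = 0.20 × 0.10 = 0.02, 50% gives 0.05, and only 100% gives 0.10. For scale, 200 per arm detects (1.96 + 0.84) × √(2/200) = 0.28 SD at 80% power.

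**The case against.** The strongest reply is that the conflict is partly loose wording. Section 4 says where data come from; 7.6 mainly says who records them. The list in 7.6 includes the trial ID number, which comes from the trial's own log, so the notes may be shorthand for hospital records in general. That narrows the conflict for drug data, but falls and, on the wording, stay still have two named sources.

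A reader might go further than the documents allow in four ways.

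- *All three secondary outcomes are equally at risk.* Dates and charted doses leave little to judgement; falls are the real exposure.
- *The allocating nurse helps score the primary outcome.* Section 7.6 says only that the nurse provides the questionnaire. The helper could be a relative or ward staff. The text names a role, so the tasks may fall to different people, although nothing requires that.
- *The primary test has a 17% error rate.* That needs a 0.10 SD shift averaged over the whole arm. Under an assumed 20% assisted, each moved by 0.10 SD, it is about 5.5%.
- *Unequal searching would produce a significant falls result.* With an assumed 8 true fallers per arm, finding all in controls and 75% in the intervention arm gives 8 v 6. That is a spurious 25% reduction in the estimate, but Fisher's exact p is 0.79.

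It is also true that patients know their arm and rate their own sleep, so much of the bias in the primary outcome cannot be removed by changing who collects it.

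**Conclusion.** The point holds in a limited form. Sections 4 and 7.6 conflict on the source of three secondary outcomes, and the 7.6 route puts a discretionary search in the hands of a role that knows the arm. The avoidable risk lies mainly with falls, where it matters for safety as well as benefit. The likely effect there is a distorted estimate rather than a false significant result: about 7-8% false positives at 3-5% risk even with a wide capture gap of 95% v 75%.

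For the primary outcome, unblinded help is left open, not planned. Its effect could run from negligible (5.5%) to material (17%), depending on an assisted share and a shift that the documents do not give. Every size here is an illustration under stated assumptions; none is an estimate of bias in this trial. The case for change rests on the conflict and the low cost of removing it.

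**What to change.** 1. **Amend 7.6 to match section 4.** Draw stay, zopiclone doses and falls from the named systems in one uniform extract by hospital number, for all participants whose data may be used under 6.2 and 7.2. The ID log in section 11.2 already links hospital and trial numbers; run the extract before that log is destroyed. Allow no discretionary search of the notes, and merge the arm only after the extract is locked. A separate arm file does not blind a nurse who already knows the arm; the protection comes from the fixed query.
2. **Questionnaire.** Patients complete it themselves where able. Where help is needed, items are read word for word, preferably by someone other than the allocating nurse where existing staff allow, and the form records who helped. Full masking is not achievable, since the form also asks about use of the aids.
3. **Analysis.** Report assistance by arm. Treat any comparison limited to unassisted patients as exploratory, because assistance arises after randomisation and may differ by arm.
4. **State in 7.4** who does and does not know the allocation.

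The cost is wording, one field on the form, one data request and one descriptive table, which suits the £10,500 budget in section 14.1. One downside is that central falls data may miss falls written only in free text, probably but not certainly to a similar degree in both arms. Bias from unmasked patients rating their own sleep remains and should be acknowledged in the report.

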#### 7.7. Discontinuation/Withdrawal of Participants from Study

Each participant has the right to withdraw from the study at any time. In addition, the Investigator may discontinue a participant from the study at any time if the Investigator considers it necessary for any reason including:

- Ineligibility (either arising during the study or retrospectively having been overlooked at screening)
- Withdrawal of Consent
- Allergy/ adverse event from intervention

If a patient withdraws, or is withdrawn, the reason will be recorded. If a patient dies during the admission, this will be recorded and the certified primary cause noted.

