### 10.3. Analysis of Outcome Measures

All participant data will be used excluding those that withdrew consent or did not complete the study questionnaire.

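### Section 7.7 does not separate stopping the aids from leaving the study, so adverse-event removals can fall on the intervention arm alone

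*Combined protocol and SAP*

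**What the plan says.** Section 7.7 states that "the Investigator may discontinue a participant from the study at any time if the Investigator considers it necessary for any reason including" three listed reasons: "Ineligibility (either arising during the study or retrospectively having been overlooked at screening", withdrawal of consent, and "Allergy/ adverse event from intervention". For what follows, it says "If a patient withdraws, or is withdrawn, the reason will be recorded", and that a death during the admission and its cause are noted. It has no category for a patient who stops using the aids but stays in follow-up, and it does not say that outcomes are still collected after discontinuation.

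Section 10.3 defines the analysis set: "All participant data will be used excluding those that withdrew consent or did not complete the study questionnaire". No intention-to-treat rule is stated anywhere.

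Three other places bear on this:

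- Section 7.4 has blinding in its title but describes none, and the nurse learns the allocation on opening the envelope: "the SleepSure research nurse will go to the next envelope in the box and open it to determine if the patient is in the control" (the sentence goes on to name the other arm). After allocation, and only in the intervention arm, the nurse is to "explain their use, checking that the patient can use and remove them safely giving instruction as required".
- Section 6.2 has as an inclusion criterion "Be able to understand and use earplugs and eye mask".
- Sections 5 and 13.7 give controls routine care and nothing else.

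**The concern.** The trial asks whether providing the aids improves sleep (section 3), so patients who have an adverse event from them are part of the answer. Under 7.7 such a patient may be taken out of the study altogether. If that happens before the questionnaire, there is no primary outcome, and 10.3 then drops the patient from every comparison, including length of stay, falls and zopiclone, although those come from routine records. Controls have no matching exit. If the removed patients slept worse than those who remain, the remaining intervention patients look better than the group that was randomised.

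Ineligibility found after randomisation is a weaker form of the same problem. It can occur in either arm. However, ability to use the aids is an eligibility item, and a hands-on check of it takes place after allocation in one arm only, so problems are more likely to come to light there.

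Changing 10.3 alone would not solve this, because an outcome that was never collected cannot be put back.

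**Working it through.** **The plan's own figure.** Section 10.2 gives 400 patients as a feasibility estimate, without effect size, SD, alpha, power or loss rate, so it cannot be reproduced. For scale only, with an assumed two-sided alpha of 0.05 and 200 per arm, the difference detectable with 80% power is (1.960 + 0.842) × √(2/200) = 0.28 SD.

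**Following a discontinued patient through the text.**

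| Situation | Primary outcome | Under 10.3 |
|---|---|---|
| Discontinued before the questionnaire | Need not be offered | Excluded as a non-completer |
| Discontinued after completing it, consent not withdrawn | Collected | Stays in on a literal reading |
| Stops using the aids, not discontinued | Collected if the questionnaire is filled in | Stays in |

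Only the first row produces the loss.

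**Illustration of size.** All inputs below are assumptions: no true effect, and a fraction q removed from the intervention arm only.

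*Form A, by correlation.* Let ρ be the correlation between the tendency to be removed and a standard normal sleep score. Then bias = ρ × φ(z_q)/(1 − q), in SD units. The false-positive rate comes from a normal approximation, allowing for the reduced variance among those who remain. For q = 2% (4 of 200) and ρ = 0.5:

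- Bias: 0.5 × 0.0484/0.98 = 0.0247 SD.
- Variance in the remaining 196 patients: about 0.974.
- Standard error: √(1/200 + 0.974/196) = 0.0998.
- Ratio of bias to standard error: 0.247.
- False-positive rate: P(Z > 1.713) + P(Z < −2.207) = 0.043 + 0.014 = 0.057.

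A simulation of 20,000 trials gave 0.024 SD and 0.057.

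*Form B, by gap.* If the removed patients sleep 1 SD worse than those who remain, bias = q × 1 SD. For q = 5% (10 of 200):

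- Bias: 0.05 SD.
- Standard error: √(1/200 + 1/190) = 0.1013.
- Ratio: 0.494.
- False-positive rate: P(Z > 1.466) + P(Z < −2.454) = 0.071 + 0.007 = 0.078.

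The two forms agree in scale. Since bias is q times the gap, the 2% example implies a gap of 0.0247/0.02, or about 1.2 SD.

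**Range under Form A** (bias in SD; false-positive rate):

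| q | ρ = 0 | ρ = 0.5 | ρ = 1 (exactly the poorest sleepers removed) |
|---|---|---|---|
| 1% | 0; 0.050 | 0.01; 0.052 | 0.03; 0.059 |
| 2% | 0; 0.050 | 0.02; 0.057 | 0.05; 0.080 |
| 5% | 0; 0.050 | 0.05; 0.084 | 0.11; 0.204 |

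With ρ = 0 the only cost is precision: power at 0.28 SD falls from 80.0% to 78.9% at q = 5%.

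**After the fix.** If no one is lost by this route, q = 0: the route adds no bias, and the sample size is unchanged.

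**The case against.** The best defence is that the design expects patients who have trouble with the aids to stay in. Section 7.7 permits discontinuation and does not require it. Section 5 says that all patients get the questionnaire. Section 10.1 plans to analyse reported problems with the aids, and the objectives count how many patients choose to use them. Section 10.3 does not name investigator discontinuation as a ground for exclusion. Section 3 rates allergy 1 out of 5 for likelihood, and only removals in the short interval before the questionnaire matter. All of this stands, and it is why the effect is probably small. It does not close the gap: 7.7 ends participation in the study, and nothing says that a discontinued patient is still followed.

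A reader might infer four stronger things that the documents do not support:

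- *That the investigator is unblinded.* The text shows that the research nurse knows the arm; it does not say what the investigator knows.
- *That both reasons lose patients unequally.* This is built in only for adverse events. For ineligibility it is a risk, and 7.4 answers difficulty in using the aids with instruction; it does not mention removal.
- *That patients who dislike the aids are removed.* The listed reason is allergy or an adverse event. Someone who dislikes the aids can simply not use them, and the trial measures that.
- *That the distortion is large.* Removing 10% (20 of 200) who sleep 1 SD worse would shift the result by 0.10 SD and give a false-positive rate of 0.164, but nothing in the documents points to a removal rate of that order or to a 1 SD gap.

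**Conclusion.** The point holds as a defect of wording with a one-sided consequence. Section 7.7 treats leaving the study as the response to an adverse event that only one arm can have, and 10.3 then drops anyone whose questionnaire was never obtained. The likely direction favours the intervention, on the assumption that removed patients slept worse. The size cannot be known from the documents. With 2% to 5% removed and the middle assumptions above, the bias is about 0.02 to 0.05 SD, against a detectable difference of 0.28 SD, and the false-positive rate is about 0.057 to 0.084. It is nil if removal is unrelated to sleep. These figures rest on assumed removal rates, an assumed link with sleep, an assumed alpha of 0.05 and 200 per arm. Low severity, but worth correcting because the rule sets no limit on removals and the correction is cheap.

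**What to change.** Amend 7.7 so that stopping the aids, or being found ineligible after randomisation, does not by itself end participation in the study. Such patients are still offered the questionnaire, their routine hospital data are still collected, and they are analysed in the arm to which they were allocated. The clinical decision to stop the aids is unchanged.

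This must stay within the existing consent rules. Section 6.2 bars data from patients who cannot consent when the questionnaire is filled in, and section 7.2 treats an unfilled questionnaire as refusal of consent for the use of that data. A rule that only the patient's own withdrawal ends data collection would conflict with both.

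Also:

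- Add a sensitivity analysis that leaves out patients ineligible on facts recorded before randomisation. The check of safe use made after allocation should not count for this, because it is made in one arm only.
- Report exclusions by arm, with reasons and whether they came before or after the questionnaire.
- Align 10.3 with 7.7 by stating how patients discontinued by the investigator are analysed.

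The cost is a protocol amendment, with approval under section 13.3 if it is judged substantial, and a few more questionnaires.
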